11.3. Quality of Life

As a sub-aim, we will investigate whether a decrease in pain impacts QoL (SF-36) over time by correlating the change in pain scores to the change in each variable between initiation of

TENS for Neuropathic Pain in NMOSD

Principal Investigator: [name], PhD

treatment through the use of single variable regression. As an additional exploratory analysis we will categorize patients as having improved pain ($> 20\%$ point change on NPS scale) or not. We will then test for a relationship between improved pain and QoL, with the hypothesis that patients with less pain will be less likely to experience anxiety and depressive symptoms.

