2.3. Secondary

Six secondary objectives are intended to collect additional information about the potential benefit of QUELL FLEX:

- A. The difference in pain scores at the end of the open label phase compared to the end of the initial blinded phase.
- B. A change in the “worst” pain score in the treatment arm vs. the sham arm between the baseline screening call and week 4; and the change in the “worst” pain from baseline to week 8 for all subjects.
- C. A change in the “average” pain score in the treatment arm vs. the sham arm between the baseline screening call and week 4; and the change in the “average” pain from baseline to week 8 for all subjects.
- D. The number of patients who withdraw because of poor compliance. We expect a higher withdrawal and non-compliance rate in the sham group.
- E. Quality of life surveys will be conducted before and after the treatment phase and at the end of the study to determine if the QUELL FLEX treatment impacts overall quality of life.
- F. Reduction in pain medication use over the course of the study.

TENS for Neuropathic Pain in NMOSD

Principal Investigator: [name], PhD

3. Hypotheses

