3.2. Secondary

- QUELL FLEX therapy is an acceptable treatment measured by compliance and patient survey.
- Patients who were randomized initially to the sham arm will show a reduction in pain score after crossing over into the open label arm. In contrast, the patients in the treatment arm will not necessarily show additional benefit after rolling over in the open label arm.
- The “average” and “worst” pain scores will decline in the treatment arm and not necessarily in the sham arm.
- As pain is a primary driver of quality of life, quality of life will improve with treatment compared to sham.
- Patients for whom QUELL FLEX works well may choose to reduce their intake of pain medications.

4. Background and Rationale

4.1. Etiology and current treatment of central neuropathic pain in patients with neuromyelitis optica spectrum disorder

Neuromyelitis optica spectrum disorder (NMOSD) is an autoimmune disease of the central nervous system (CNS) that preferentially causes recurrent inflammatory attacks in the optic nerves and spinal cord, leading to blindness, paralysis and death. Despite these devastating consequences of the disease, patients have reported that pain is among the most prevalent and debilitating symptoms.

In particular, central neuropathic pain (CNP) is pervasive, severe, intractable to treatment, and affects 62-91% of patients with NMOSD. CNP is described as agonizing burning, stabbing, shooting, tingling or squeezing

Figure 1. Cross-section of the spinal cord depicting spinal tracts.

From:

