6.5.1.1. Treatment Days

1. Prior to initiation of Quell therapy, patients will be asked to rate their pain on the Numerical Pain Scale and will complete a Short Form-36 Health Inventory (SF-36).
2. All training on the use of the device will be conducted remotely through Zoom.

TENS for Neuropathic Pain in NMOSD

Principal Investigator: [name], PhD

3. Patients will be shipped a QUELL FLEX device. It will either be a functional QUELL FLEX device for the treatment arm or a non-functional QUELL FLEX device in the sham arm. All of the lights, charging equipment, and app connectivity will be the same. The only difference is that the non-functional sham devices will administer an electrical current for only 2 minutes each at the top of a treatment hour, at 30 minutes and at 58 minutes, as opposed to for the full hour when the device is engaged.
4. Patients will be informed that we are conducting a number of different treatment paradigms – some of them have high frequency waves that are not perceptible, and some have lower frequency waves that may be transiently perceptible. In addition, we will re-inform them there is a sham arm.
5. The electrodes will be placed on patients on the back in the dermatome of the most painful area. The intensity of the stimulus is increased until the patient can first feel some sensation associated with the electrodes. Script: “Tell me when you feel something.”
6. Stimulation intensity will be increased until a maximum threshold is tolerated without being painful.
7. Once the intensity is at its maximum setting, the study coordinator will evaluate the level of pain. If the patient feels a constant burn, single sting or feeling of discomfort, the electrodes will be repositioned. The exact electrode positioning will depend on the delimitation of the surface pain area, and analgesic response of the patient.
8. Once satisfactory electrode placement and stimulus intensity is determined, therapy is maintained for at least an hour per day for 4 weeks (both treatment and sham groups).
9. Patients will report pain scores weekly throughout experimental period while on a zoom call with the trial researcher. Patients will again complete all measurement tools and pain ranking at end of treatment.

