11.1. Acceptability

Counts and percentages will be used to assess acceptability based on adherence to treatment schedule. We will report the number and percent of patients in each group who are able to complete all treatments. A chi-square test for independence of group by dichotomous outcome will be performed to assess differences between the two groups. In the event that the expected frequencies are < 5 , Fisher's exact test will be performed. While no serious adverse events have been reported with use of Scrambler or other TENS therapies in the NMOSD patient population, the numbers and percent observed for each group will be reported.

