11.2. Efficacy

Change in pain score will be calculated by subtracting the patient's week 4 score from his or her baseline value prior to treatment initiation. Change in scores will be summarized using means and standard deviations provided the resulting distribution is symmetric, otherwise medians and interquartile ranges will be used. Provided the resulting distribution of pain scores is roughly normal, we will use a two-sample t-test to compare the QUELL FLEX and sham groups. Previous studies suggest that the average pain value at baseline is at least 4 on the 0-10 numerical rating scale with a standard deviation of the original pain value expected to fall in the range of 1-1.5 in this patient population. As such, a conservative estimate of the standard deviation would be approximately 20%. With 19 patients in each arm and under these assumptions, we will have the ability to detect a change of 2.0 points in the QUELL FLEX group with power of 0.90. If the change score distribution is highly skewed, Wilcoxon's signed rank test will be utilized instead.

To account for ~20% dropout rate, we will add 4 subjects to each arm for a total of 23 subjects per arm. We included a dropout rate of ~20% based on previous studies with this device. We will run a sensitivity analysis to determine if the drop-out rate in either arm had an impact on the trial results.

A 20% reduction in pain has been previously determined to be a clinically meaningful improvement, we will report the number and percent of patients from each group who achieve this benchmark.

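### The plan hypothesises that quality of life improves relative to sham but specifies no SF-36 comparison by randomised arm

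*Combined protocol and SAP*

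**What the plan says.** All references are to the combined protocol and SAP.

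- **Hypothesis (Section 3.2):** "quality of life will improve with treatment compared to sham". This is explicitly a comparison between arms.
- **Objective E (Section 2.3):** SF-36 surveys are done "to determine if the QUELL FLEX treatment impacts overall quality of life". The timing is before treatment, after the treatment phase and at the end of the study.
- **Data collection (Sections 6.5.1.1, 6.5.1.2 and 9.2):** SF-36 is completed in both arms before treatment, at the end of the blinded four weeks and at the end of the open-label phase.
- **Analysis (Section 11.3):** the sub-aim is addressed by "correlating the change in pain scores to the change in each variable between initiation of" treatment, "through the use of single variable regression". An exploratory analysis then classifies patients by pain improvement: "We will then test for a relationship between improved pain and QoL".
- **Between-arm analyses elsewhere:** Section 11.1 plans "A chi-square test for independence of group by dichotomous outcome will be performed to assess differences between the two groups", where the outcome is completion of treatments, and reports serious adverse events by group. In Section 11.2, "we will use a two-sample t-test to compare the QUELL FLEX and sham groups", and the outcome is change in pain score. Section 11.4 deals only with replacing patients who never start.

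**The concern.** The hypothesis concerns treatment against sham, while the specified analyses concern pain against quality of life. Those are different questions. If pain and SF-36 move together in every patient whatever device is worn, both 11.3 analyses will be positive although the device has no effect. SF-36 itself contains pain items (Appendix A), which makes some association likely. Such results cannot support a claim of benefit over sham, yet they are the only SF-36 results the plan would produce.

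If the comparison is left to be filled in later, the score, time point and method would be chosen during or after the trial. Section 6.4 opens the allocation envelopes block by block, so some assignments will be known before the last patients finish.

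Two details of 11.3 add to this:

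- The change window has a start and no stated end. If it ran to week 8, it would include four weeks in which every patient has a functional device (6.5.1.1, items 10 and 11).
- No main SF-36 score is named among the several the questionnaire can produce.

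**Working it through.** **1. Does any planned analysis compare SF-36 by arm?** The documents give no SF-36 sample size, effect or SD, so there is no plan figure to reproduce. The check is on the text.

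| Section | Outcome | Compared across | SF-36 by arm? |
|---|---|---|---|
| 11.1 | Completion of treatments; serious adverse events | Arm | No |
| 11.2 | Pain change; 20% pain responders | Arm | No |
| 11.3, regression | SF-36 change | Pain change (single predictor) | No |
| 11.3, exploratory | SF-36 | Pain improved or not | No |
| 11.4 | None (replacement rule) | – | No |

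The general reference to score changes in 11.2 stands between two sentences about pain scores, so it cannot fairly be read as including SF-36. The generic dichotomous test in 11.1 belongs to acceptability and does not fit SF-36 scale scores. A regression with one predictor leaves no place for an arm term.

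**2. Can the 11.3 regression be positive with no device effect?** Simulation with 38 patients pooled (2 × 19), no treatment effect, and an assumed correlation between pain change and SF-36 change of 0.3, 0.5 or 0.7 gave a significant regression in about 46%, 91% and 99.9% of trials.

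**3. What could the missing comparison show?** Assumptions, none given in the documents: two-sided 0.05, SF-36 SD = 1 at both visits, true difference 0.5 SD, baseline-to-week-4 correlation ρ = 0, 0.5 or 0.7. Numbers per arm are n = 19 (evaluable) and n = 23 (enrolled), from 11.2.

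- Baseline-adjusted: residual SD s = √(1 − ρ²), df = 2n − 3.
- t-test on change: s = √(2(1 − ρ)), df = 2n − 2.
- 95% CI half-width = t(0.975, df) × s × √(2/n). Power is from the noncentral t with noncentrality 0.5 / (s√(2/n)).

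Example, baseline-adjusted, n = 19, ρ = 0: √(2/19) = 0.324, t(0.975, 35) = 2.030, half-width = 2.030 × 1 × 0.324 = 0.659. Noncentrality = 0.5/0.324 = 1.54, power 0.323.

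| Method | n per arm | Power at ρ = 0, 0.5, 0.7 | Half-width (SD) at ρ = 0, 0.5, 0.7 |
|---|---|---|---|
| Baseline-adjusted | 19 | 0.323, 0.409, 0.555 | 0.659, 0.570, 0.470 |
| Baseline-adjusted | 23 | 0.381, 0.482, 0.641 | 0.595, 0.515, 0.425 |
| t-test on change | 19 | 0.186, 0.323, 0.491 | 0.931, 0.658, 0.510 |
| t-test on change | 23 | 0.217, 0.382, 0.572 | 0.841, 0.594, 0.460 |

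Simulating the baseline-adjusted analysis (20,000 runs per setting) gave slightly lower power: 0.315, 0.401, 0.548 for n = 19 and 0.372, 0.471, 0.626 for n = 23. The false-positive rate was 0.049–0.052.

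**4. Why name one score?** As an illustration only, take one score for each of the seven distinct headings in Appendix A and test each by arm at 0.05 with no effect. If the scores are independent, the chance of at least one significant result is 1 − 0.95⁷ = 0.302. By simulation it is 0.272, 0.229 and 0.178 at inter-score correlations of 0.3, 0.5 and 0.7.

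**The case against.** The strongest reply is that the comparative claim rests on one bullet in Section 3.2. Objective E is not worded by arm, although objectives B and C in the same list are. Section 11.3 already calls its analyses a sub-aim and exploratory, and does not offer them as evidence against sham. This is true and limits the seriousness: the outcome is secondary and unpowered, and the primary endpoint is untouched. But the hypothesis in 3.2 is explicit, and no section tests it.

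Other objections affect only the edges:

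- The 11.3 sentence runs across a page break, so an end point might have been lost. It reads across the break without evident loss of words, but the point is subsidiary.
- The power and seven-score figures describe an added test, not a defect in the plan's own numbers. They are context, and the omission does not depend on them.
- Section 6.8 continues follow-up after discontinuation unless the patient refuses, but 6.5.1.1 item 9 ties the questionnaires to the end of treatment. A week-4 SF-36 in patients who stop early is therefore implied and not explicitly required.
- The drop-out sensitivity analysis in 11.2 refers to the trial results generally and might already include SF-36. Saying so would remove the doubt.

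**Conclusion.** The concern holds. Of the two SF-36 analyses specified, none uses randomised arm, so the plan as written gives no estimate for its hypothesis of improvement relative to sham. That conclusion is textual and needs no assumption.

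The size of what could be learned does rest on the assumptions above. For a 0.5 SD difference, power runs from about 19% (change score, 19 per arm, ρ = 0) to 64% (baseline-adjusted, 23 per arm, ρ = 0.7). The comparison will mainly provide an estimate with a wide interval. That argues for reporting the interval, not for omitting the randomised comparison. The change should be made, as a secondary matter.

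**What to change.** In Section 11.3:

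1. Make the main quality-of-life analysis a between-arm comparison of week-4 SF-36 adjusted for baseline SF-36. The minimum alternative is a two-sample t-test on baseline-to-week-4 change, matching the method for pain in 11.2. Report the estimate with a 95% CI.
2. Include all randomised patients with a week-4 SF-36, including those who stopped using the device, and state how this set relates to the replacement rule in 11.4. Confirm that the week-4 SF-36 is sought from patients who stop early.
3. Name one main SF-36 score and its scoring method before any unblinded SF-36 data are examined. Treat the other scores as descriptive.
4. State that the drop-out sensitivity analysis in 11.2 covers this comparison.
5. Fix the window of the pain–SF-36 regression at baseline to week 4. Label it exploratory and not evidence of benefit over sham.
6. State that a null between-arm result would not show absence of effect.

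A minor wording point: 11.2 counts a 20% reduction in pain as improvement, while 11.3 uses a change of more than 20% points on the scale. Use one definition.

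The cost is plan wording, with no added visits or questionnaires beyond those scheduled. The downside is imprecision: half-widths of about 0.42–0.66 SD if baseline-adjusted and 0.46–0.93 SD on change scores. Baseline adjustment also differs from the t-test planned for pain. The change-score version avoids that difference but has lower power over the range examined.

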11.4. Reporting and Exclusions

Patients who sign a consent form, but do not initiate protocol intervention for any reason (e.g., patients who are screen failures), will be replaced and will not count towards our accrual goal.

TENS for Neuropathic Pain in NMOSD

Principal Investigator: [name], PhD

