2.1. Scheme

Patients will be randomized 1:1 to receive treatment daily for 4 consecutive weeks versus sham, followed by an open-label phase for additional 4 consecutive weeks.

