6.3. Determination of Eligibility

Eligibility for participation will be reviewed and confirmed by a member of the study staff. Upon successful eligibility, the patient will be eligible for registration into the study, at which time a study-specific subject ID/number will be assigned.

For patients who reach the study team from outside of the Mass General NMO Clinic, a member of the patient's care team will be consulted to confirm that s/he believes that the participant is appropriate for protocol participation.

Study intervention cannot begin until the patient is successfully registered and consented.

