6.4 Randomization and Blinding

Randomization would be done in blocks of 4 (e.g. 2 placebo and 2 treatment assignments) assigned at random at the beginning of the study for each 4 patients enrolled in the study consecutively. This ensures that it is not possible to predict the arm assignment of patients as we unblind them in groups of 4 at the conclusion of each patient's participation in the study.

Blinding keys, including the arm assignment of the patient, will be sealed in envelopes and not opened until unblinding occurs for the 4-patient-block.

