6.8. Discontinuation and Withdrawal of Subjects

All patients who initiate protocol intervention will be included in the overall evaluation of tolerability and acceptability (intent-to-treat analysis). All reasons for discontinuation of therapy will be clearly documented in the record.

Unless the subject refuses, follow-up will continue for the planned duration following the study intervention.

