6.8.1. Discontinuation of Intervention

The reasons for discontinuation of protocol treatment include:

- Non-compliance with the study protocol; including, but not limited to not using the device more than 75% of the study duration.
- Unacceptable major reaction to electrical stimulation or other major adverse events
- Intercurrent illness or condition that would, in the judgment of the treating investigator, affect assessment of clinical status to a significant degree or require discontinuation of study intervention.
- At subject's own request. Note: The reason for discontinuation from the study must be documented. The patients will be included in the overall evaluation of tolerability and acceptability (intent-to-treat analysis) if any protocol intervention was administered prior to withdrawal.
- Study is closed or cancelled for any reason.

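### Section 11.4 lets randomised patients who never start the device be replaced, so the acceptability set that 6.8 calls intent-to-treat holds initiators only

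*Combined protocol and SAP*

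**What the plan says.** All references are to the combined protocol and SAP.

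- **Replacement (11.4).** "Patients who sign a consent form, but do not initiate protocol intervention for any reason (e.g., patients who are screen failures), will be replaced". Screen failure is given as an example, not as a limit. The sentence ends by saying that these patients "will be replaced and will not count towards our accrual goal".
- **Analysis set (6.8).** "All patients who initiate protocol intervention will be included in the overall evaluation of tolerability and acceptability (intent-to-treat analysis". Section 6.8.1 repeats the condition for patients who leave at their own request: they are included "if any protocol intervention was administered prior to withdrawal".
- **Assignment (2.1, 6.4).** Allocation is 1:1, in blocks of 4, "assigned at random at the beginning of the study for each 4 patients enrolled in the study consecutively".
- **Shipping (6.5.1.1, step 3).** "It will either be a functional QUELL FLEX device for the treatment arm or a non-functional QUELL FLEX device in the sham arm". Electrode placement and intensity setting follow in steps 5 to 7, and step 8 describes the daily therapy.
- **Acceptability (3.2, 11.1).** Acceptability is a secondary hypothesis. Section 11.1 reports, by group, the number and percentage of patients who complete all treatments, and compares the groups. It states no denominator of its own.
- **Efficacy (11.2).** No analysis population is named. A sensitivity analysis for drop-out is promised without detail.

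**The concern.** An intent-to-treat set normally contains everyone randomised, in the arm assigned. Here the label goes to a set defined by what patients did after they were assigned. For a device that patients apply themselves at home after remote training, receiving it and never switching it on is a plain failure of acceptability. The replacement rule takes such patients out of the accrual count, the initiators-only definition takes them out of the acceptability evaluation, and no section asks for them to be reported by arm. At stake are the accuracy of the label and the denominator of the completion percentage in 11.1.

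**Working it through.** **1. Can a patient be randomised and not start?** Section 6.3 says "Study intervention cannot begin until the patient is successfully registered and consented", which puts registration and consent before the intervention but gives no time for randomisation. Section 6.4 ties assignment to consecutive enrolment. Step 3 of 6.5.1.1 ships either an active or a sham unit, so the arm must be known when the parcel leaves. There is therefore a window from assignment to first use. This is inferred from the shipping step; no section states it.

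**2. What happens to a patient lost in that window?** Under 11.4 the patient is replaced and not counted. Under 6.8 and 6.8.1 the acceptability set consists of patients who initiated or were given some intervention. Since 11.1 gives no other denominator, the patient is absent from the completion percentage.

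**3. The plan's accrual figure.** Section 11.2 takes 19 per arm, allows for about 20% dropout and adds 4, giving 19 + 4 = 23 per arm and 46 in total. Check: 19 × 1.20 = 22.8, rounded up to 23; 19 / (1 − 0.20) = 23.75, rounded up to 24. The stated 23 reproduces to within one patient. Under 11.4 these are 23 counted patients per arm, so the number randomised in an arm can be 23 + k, where k is the number of replaced non-starters.

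**4. Effect on the completion percentage.** With c completers among n counted patients, the plan reports c / n. On all randomised patients the figure is c / (n + k). For any k above 0 the second is smaller, so the omission works in one direction only. The documents give neither c nor k. Illustration with assumed values c = 20 and n = 23:

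| Non-starters k | All randomised | Percentage | Difference from 87.0% |
|---|---|---|---|
| 0 | 20/23 | 87.0% | none |
| 1 | 20/24 | 83.3% | about 4 points |
| 2 | 20/25 | 80.0% | 7 points |
| 3 | 20/26 | 76.9% | about 10 points |

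**5. What the fix could cost in power.** Assumptions: the 20% standard deviation in 11.2 is read as 2.0 points on the 0–10 scale; the difference is 2.0 points; the test is a two-sample t-test at two-sided 5% (11.2 states neither level nor sidedness). Power comes from the noncentral t distribution with 2n − 2 degrees of freedom and noncentrality 2.0 / (2.0 × √(2/n)). At 19 per arm it is 0.851. A one-sided 5% test gives 0.916; the plan states 0.90.

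- *Non-starters not replaced, week-4 scores not obtained.* Evaluable patients per arm are (23 − k) × 19/23, rounded down: 18, 17 and 16 for k = 1, 2 and 3. Power is 0.830, 0.807 and 0.781.
- *Week-4 scores obtained.* Assume 19 per arm are analysed, a share k/23 of them non-starters with no treatment benefit. The difference becomes 2.0 × (1 − k/23) = 1.913, 1.826 and 1.739. Power is 0.818, 0.782 and 0.742.

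Obtaining the scores keeps the analysis to patients as randomised. It does not win back power.

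**The case against.** The strongest reply is that 11.4 is an accrual rule aimed at screen failures, and that analysing blinded starters is a defensible choice. Several parts of that stand.

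- **Accrual, not analysis.** Section 11.4 does not say that data are discarded. The restriction comes from 6.8 and 6.8.1, and 6.8 says that initiators are included without adding that nobody else is. Read with the condition in 6.8.1 and the lack of any other denominator, exclusion is still the natural reading.
- **Scope of the label.** It covers tolerability and acceptability. A reader might infer that the primary efficacy analysis is also mislabelled. It is not: 11.2 carries no label and no defined population.
- **Bias between arms.** Because the sham unit gives current for only three 2-minute periods in the hour, a reader might infer that set-up failures differ by arm and are then removed. The documents do not support this. Set-up itself delivers current, so such a patient has probably had some intervention administered and is kept under 6.8.1, although initiation is undefined. A patient who declines before first use has a unit with the same lights, charging equipment and app connection, and the assignment is sealed (6.4), so the decision should not depend on arm while blinding holds.
- **Blocks.** A reader might infer that replacement breaks the blocks of 4. Putting the replacement in the vacated slot would keep 2:2, and 46 is not a multiple of 4 in any case. The absence of a slot rule is an operational gap, not a contradiction.

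None of this answers the core point: an initiators-only set is called intent-to-treat, and randomised non-starters need not be counted or reported.

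**Conclusion.** The point holds as one of population and reporting, and should be corrected. As written, a patient who is randomised, receives an arm-specific device and never starts it is replaced and left out of the acceptability denominator. The intent-to-treat label on that set is wrong, and the omission can only raise the completion percentage. The size is unknown and may be zero; the differences of 4 to 10 points in the illustration rest on assumed counts. The conclusion depends on one inference, that assignment precedes first use, which the shipping of distinct devices makes strong. It does not extend to a claim of bias between arms or of a biased primary efficacy comparison.

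**What to change.** - **11.4:** replace only patients who leave after consent and before an arm is assigned. A patient with an assigned arm is not replaced and keeps the block slot.
- **6.8 and 6.8.1:** define intent-to-treat as all randomised patients by assigned arm. Call any initiators-only set modified intent-to-treat. State, for analysis purposes, that the set-up session counts as initiation.
- **11.1:** use all randomised patients as the denominator, count randomised non-starters as not completing treatment, and report their number by arm.
- **Data collection:** ask randomised non-starters for a week-4 pain score if they agree.

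The cost is a few sentences and no new visits. Non-starters would use part of the allowance of 4 per arm, which 11.2 bases on dropout in previous studies with the device and does not say covers them. Evaluable numbers could fall slightly below 19 per arm if week-4 scores are not obtained, with the modest loss of power shown above, and the completion percentage may look less favourable.
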